13 DISCONTINUATION OR WITHDRAWAL FROM TREATMENT

13.1 Discontinuation of a 50 Minute Inhalation Period (note: treatment will not be initiated if threshold values are present beforehand)

A 50 minute inhalation treatment period will be discontinued if the following occurs.

- a change in the blood pressure systolic value ≥ 20 mmHg or an absolute value of ≤ 80 mmHg repeated at 2 minutes
- an oxygen saturation of $< 85\%$ and following recheck of sensor placement
- a reduction in oxygen saturation $> 5\%$ (e.g. 98% to 92%).
- a persistent* increase in heart rate of ≥ 30 from start of a treatment or an absolute value of 150
- a persistent* absolute increase in methemoglobin of more than 5% above the Day 1 baseline value and following recheck of sensor placement
- a recorded inspired NO₂ > 5 ppm during any treatment
- Subjects with methemoglobin of more than 15% should be treated with 100% oxygen. If 20% or greater, subjects should be treated with Methylene Blue (1 to 2 mg/kg intravenously). Repeat in one hour if necessary. Note: Inject intravenously very slowly over a period of several minutes to prevent local high concentration of the compound from producing additional methemoglobin. Large intravenous doses of Methylene Blue may produce nausea, abdominal and precordial pain, dizziness, headache, profuse sweating, mental confusion and the formation of methemoglobin. Also note that methemoglobin cannot be measured by the oximeter after treatment with methylene blue and should be measured by blood values. See package insert for full contraindications and side-effects. Methylene blue is contraindicated in patients who have developed hypersensitivity reactions to it and in severe renal insufficiency. It is relatively contraindicated in G6PD deficient patients as it can cause severe hemolysis and also in patients with Heinz body anemia. In such cases it may be appropriate to treat with intravenous ascorbic acid.

*Persistent means that the value was obtained on a repeated measurement taken 5 minutes following the original measurement.

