13.2 Withdrawal from study

If a subject experiences any of the following events during the study period, they should be immediately be withdrawn from the study.

Study drug related adverse events:

- Two consecutive inhalation treatment periods with a persistent absolute increase in methemoglobin of more than 5% above the Day 1 baseline value
- Study drug related significant hemoptysis: production of greater than 50 mL blood in a 24 hour period. Note: Standard treatment for significant hemoptysis should include immediate chest x-ray, hematocrit measurement and if frothy sputum present, an evaluation for hemosiderin labeled macrophages.
- Any study drug related adverse event that repeats upon treatment continuation.

NO-NTM

Other withdrawal criteria:

- At the discretion of the subject
- At the discretion of the Investigator, if deemed appropriate, for any reason
- Subjects will also be withdrawn from the study if they have had to discontinue treatment during the 50-minute inhalation period more than twice due to criteria listed in 13.1.

If a subject is withdrawn because of an adverse event, the subject will be followed and treated by the Investigator until the abnormal parameter or symptom has resolved or stabilized.

The adverse events must be followed to resolution and the follow-up evaluations should be performed when the subject has stabilized.

If for any reason a subject does not complete the study, the reason will be entered on the CRF. All subjects are free to withdraw from participation at any time, for any reason, specified or unspecified, and without prejudice. The Investigator must record the reason for the early termination.

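### A first methylene blue rescue at methemoglobin of 20% or more meets no mandatory withdrawal criterion, so re-dosing is left to discretion

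*Combined protocol and SAP*

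**What the plan says.** Section 13.1 concerns a single dosing session: "A 50 minute inhalation treatment period will be discontinued if the following occurs". Its list includes a persistent methemoglobin rise of more than 5 points above the Day 1 baseline, where persistent means found again 5 minutes later. The last item in the list gives the treatment of high levels: 100% oxygen above 15%, then "If 20% or greater, subjects should be treated with Methylene Blue (1 to 2 mg/kg intravenously". The section heading adds a hold before the next session: "treatment will not be initiated if threshold values are present beforehand". The same section states that the oximeter cannot read methemoglobin after methylene blue and that blood values should be used.

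Section 13.2 lists the events that require withdrawal from the study:

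- for methemoglobin, "Two consecutive inhalation treatment periods with a persistent absolute increase in methemoglobin of more than 5% above the Day 1 baseline value";
- for bleeding, one drug-related hemoptysis above 50 mL within 24 hours, so a single event is enough;
- for recurrence of other harms, "Any study drug related adverse event that repeats upon treatment continuation";
- for repeated stops, inhalations discontinued "more than twice due to criteria listed in 13.1".

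Withdrawal may also be chosen by the subject, or "At the discretion of the Investigator, if deemed appropriate, for any reason". No item in 13.2 names an absolute methemoglobin level or the use of an antidote.

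Section 12.2.5 has methemoglobin measured by pulse methemoglobinometer, continuously during each treatment and recorded every 5 minutes. For levels of 15% or higher it refers the reader to 13.1 for treatment only.

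**The concern.** The written rules are stricter for the milder event. Two modest rises in a row take the decision out of the investigator's hands. One level high enough to need an intravenous antidote does not. The plan is not opposed to single-event rules, since 13.2 has one for hemoptysis.

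What is at stake is whether a rescued subject is exposed again to the agent that caused the event. The two rules that would protect that subject at the next session are the hold and the stop for a rise above 5 points. Both are run from a device whose reading 13.1 says is not available after methylene blue. Blood values are named as the substitute, but Table 3-1 and Table 12.1 schedule no blood methemoglobin test before or during a later inhalation.

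**Working it through.** The plan states no figure on this point, so the main check sets one event against each rule. The event is one methemoglobin level of 20% or more, confirmed on repeat and treated with methylene blue. It is assumed to be the subject's first 13.1 stop, with no related adverse event of the same kind before it.

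**Mandatory criteria in 13.2**

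| Criterion | Events needed | Count after this event | Met? |
|---|---|---|---|
| Consecutive inhalations with a persistent rise above 5 points | 2 | 1 | No |
| Drug-related hemoptysis above 50 mL in 24 hours | 1 | not applicable | No |
| Drug-related adverse event that recurs on continuation | 2 (the event and its recurrence) | 1 | No |
| Inhalations discontinued under 13.1 | 3 (more than 2) | 1 | No |

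Mandatory criteria met: 0 of 4. The first, third and fourth rows can be met only after at least one further inhalation.

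**Other text that might bar re-dosing**

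- 13.1 heading: a hold that lapses once no threshold value is present.
- 12.2.5 and Table 12.1: readings every 30 minutes until return to baseline. This is a monitoring duty with no dosing rule attached.
- 12.2.7: methylene blue is in the chart of drugs excluded because they can induce methemoglobinemia. No withdrawal consequence is attached, and the matching exclusion criterion in 10.2 applies at screening.
- 12.3.2: the Medical Monitor reviews serious adverse events in real time and may temporarily stop the study. No rule is given for one subject.
- 15.1.2 and 15.1.6: a rescue would plausibly be a serious adverse event as an important medical event, and would then go to the IRB within 24 hours. Methemoglobinemia is also an event of special interest, to be monitored and recorded. Neither provision stops dosing.

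**Exposure that could remain** (section 11.1: 3 inhalations a day on Days 1-5, 8-12 and 15-19)

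- Planned inhalations = 3 x 15 = 45.
- Check against the plan's own total: 45 x 160 ppm x 50/60 h = 6000 ppm hours, which agrees with 11.1.
- Left after a rescue at inhalation k = 45 - k, so at most 44 (k = 1) and none when k = 45.
- Earliest next start: 3 hours after the end of the stopped inhalation, if no threshold value is present.

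**Weight of one subject in the primary proportion** (14.1: 6 to 10 subjects)

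- 1/10 = 10.0 percentage points.
- 1/6 = 16.7 percentage points.

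**The case against.** The strongest reply is that this is a legitimate design choice. The study is open-label, has at most 10 subjects, and gives the investigator open authority to withdraw anyone. The decision would fall to a team that has just given an intravenous antidote, and nothing instructs that team to dose again. All of this is true. It makes re-dosing unlikely, but it does not explain why the smaller, repeated rise has a fixed rule and the larger event has none.

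Second, the event is improbable. In the cited phase I study, eight adults with CF at 160 ppm reached at most 3.0%. Section 10.2 excludes G6PD deficiency, hemoglobinopathy and drugs that raise methemoglobin, and inhalation stops at a persistent rise above 5 points. This stands, and it is why the point is minor. The phase I sessions lasted 30 minutes and these last 50, so 3.0% indicates distance from 20% and is not a rate for this trial.

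Third, 44 further inhalations is a ceiling. A persistent rise at the next session, a recurrence, or a third stop would force withdrawal sooner. That also stands, but each of those protections acts only after re-exposure. Likewise, a temporary stop of the whole study by the Medical Monitor would in practice pause that subject's dosing, but it is optional and temporary.

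Three stronger readings are tempting, and the documents do not support them:

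- *A rescue has no consequence beyond the current session.* The heading of 13.1 holds the next one while a threshold value persists.
- *Re-dosing would be unmonitored.* Section 13.1 directs the use of blood values, and it does not say how long the oximeter limitation lasts. What is missing is a rule linking those blood values to the decision to dose.
- *Every rescued subject escapes mandatory withdrawal.* A rescue that is the third 13.1 stop, or that directly follows an inhalation with a persistent rise, does meet a criterion.

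**Conclusion.** The gap is real and minor. For a first 13.1 stop, a rescue at 20% or more satisfies 0 of 4 mandatory withdrawal criteria, while two consecutive persistent rises of just over 5 points satisfy one. The only fixed restraint on the next inhalation is a temporary hold, tied to a measurement that 13.1 says the usual device cannot make after methylene blue. Everything else is discretion or reporting.

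No probability of harm can be stated, because the documents give no rate for reaching 20%. The conclusion rests on the wording of sections 13.1 and 13.2 and on the first-stop condition set out in the working. It concerns subject safety only. It shows no error in the sample size or in the primary analysis. The figures of 10.0 and 16.7 points are the possible cost of the remedy and are not evidence of harm from the present plan.

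**What to change.** Add one sentence to section 13, as a treatment-stopping rule outside the list in 13.2, because that list removes the subject from the study:

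*Any subject with methemoglobin of 20% or more on repeat measurement, or given methylene blue, receives no further gNO and is followed for adverse events and the remaining scheduled visits and cultures.*

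The 20% level is the plan's own antidote threshold, and the repeat reading after 5 minutes is already required by 12.2.5. No visit, test or analysis is added, and no new rule on the endpoint or its denominator is needed for this purpose.

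The cost falls on the rescued subject, who receives fewer than the 45 planned inhalations. If that subject is still counted and would otherwise have converted, the observed conversion proportion falls by at most one subject: 10.0 points with 10 subjects, 16.7 with 6.

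Two limits remain. A subject above 15% but below 20% who needed oxygen stays under the existing rules and discretion. A rescued subject would also be followed more fully than one withdrawn under 13.2 for two smaller rises. That difference is acceptable, though the sponsor could align the two.

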13.2 Withdrawal from study

If a subject experiences any of the following events during the study period, they should be immediately be withdrawn from the study.

Study drug related adverse events:

- Two consecutive inhalation treatment periods with a persistent absolute increase in methemoglobin of more than 5% above the Day 1 baseline value
- Study drug related significant hemoptysis: production of greater than 50 mL blood in a 24 hour period. Note: Standard treatment for significant hemoptysis should include immediate chest x-ray, hematocrit measurement and if frothy sputum present, an evaluation for hemosiderin labeled macrophages.
- Any study drug related adverse event that repeats upon treatment continuation.

NO-NTM

Other withdrawal criteria:

- At the discretion of the subject
- At the discretion of the Investigator, if deemed appropriate, for any reason
- Subjects will also be withdrawn from the study if they have had to discontinue treatment during the 50-minute inhalation period more than twice due to criteria listed in 13.1.

If a subject is withdrawn because of an adverse event, the subject will be followed and treated by the Investigator until the abnormal parameter or symptom has resolved or stabilized.

The adverse events must be followed to resolution and the follow-up evaluations should be performed when the subject has stabilized.

If for any reason a subject does not complete the study, the reason will be entered on the CRF. All subjects are free to withdraw from participation at any time, for any reason, specified or unspecified, and without prejudice. The Investigator must record the reason for the early termination.

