In sum, there is sufficient preclinical evidence of antimicrobial effect of gNO on NTM. There are compelling reasons to use a gas for treatment as it may get to areas of the lung that will not be reached by antibiotics by either the systemic or inhalation route. Even in poorly ventilated lung units, a 50 minute exposure should be sufficient time for NO to achieve therapeutic levels. There are also sufficient safety data that the proposed exposure should be well tolerated. It is premature to predict how this therapy will be best used, but multiple options could be conceived such as eradication of first infection (especially for Mabs), improving outcomes when used in conjunction with standard antibacterial regimens, shorter durations of treatment regimens, among others. This study proposes to demonstrate that there can, indeed, be a killing effect of NTM as well as assess for how quickly it may return in sputum cultures as these will be key factors in designing subsequent treatment trials.

7 **STUDY OBJECTIVE**

The short term goal of this proposal is a proof-of-concept study in which we will expose patients with NTM lung disease and who have persistently positive sputum cultures to test the feasibility of this therapy in this population as well as the safety and efficacy of the therapy.

8 **STUDY ENDPOINTS**

- The primary measure of efficacy will be sputum culture for mycobacteria converted to negative at completion of treatment.
- Secondary measures of efficacy will include assessment of feasibility of this treatment (i.e. recruitment, completion, and satisfaction), sputum culture results for mycobacteria at 3 months following completion of treatment, and safety and tolerability assessments based on adverse events (AEs) and point of care testing for arterial oxygen saturation and methemoglobin levels.

9 **STUDY DESIGN**

9.1 **Overview of Study Design**

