Sputum will be collected for culture at Screening, and Days 5, 12, and 19 (treatment dates), and Weeks 7, 11 and 15 (follow up). Sputum samples will be processed at the MUSC clinical laboratory, using standard decontamination procedures, fluorochrome microscopy, solid medium culture on a biplate of Middlebrook 7H10 agar with and without antibiotics, and a broth culture (BACTEC 960 [Becton Dickinson, Sparks, MD] or ESP [TREK Diagnostic Systems, Cleveland, OH]). MAC isolates are identified with AccuProbe (Hologic-GenProbe, San Diego, CA).

Semiquantitative AFB smear and culture results for each submitted clinical specimen will be recorded [Wallace 1996]. Briefly, a negative culture exhibits no mycobacterial growth. Cultures will be reported as positive if growth occurs in broth medium only; growth on broth medium plus solid medium cultures with countable colonies will be reported as 0–49 colonies, 1+; solid medium growth with 50–99 colonies, 2+; solid medium growth with 100–199 colonies; 3+, solid medium growth with 200–299 colonies; and 4+, solid medium growth with at least 300 colonies. For data analysis, each culture will be scored as follows: 0, no growth in broth or solid medium; 1, broth medium growth only; 2, countable colonies (<50 colonies) on solid medium; and 3–6, 1+ to 4+ growth on solid medium, respectively.

12.5.1**Quality of life measures**

Validated instruments will be used for measurement of symptoms and quality of life. Since study subjects may have different underlying conditions, for which there are different quality of life measures, we will use a condition specific measure for each as follows:

NO-NTM

- Cystic fibrosis: Cystic fibrosis Questionnaire-Revised (CFQ-R)
- Bronchiectasis: Quality of Life – Bronchiectasis (QOL-B)
- All: St. George's Respiratory Questionnaire (SGR-Q)
- All: Leicester Cough Score

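### Section 13.2 takes subjects out of the study rather than only off gNO, and no early-termination culture is scheduled, so the end-of-treatment primary culture can be lost

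*Combined protocol and SAP*

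**What the plan says.** Section 13.2 is titled as withdrawal from the study. Of subjects with a listed drug-related event it says that "they should be immediately be withdrawn from the study". The listed events are:

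- two inhalations in a row with a persistent metHb rise of more than 5% absolute over the Day 1 baseline;
- drug-related hemoptysis of more than 50 mL in 24 hours;
- a drug-related adverse event that comes back when treatment continues.

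A separate line extends study withdrawal to stopped inhalations: "Subjects will also be withdrawn from the study if they have had to discontinue treatment during the 50-minute inhalation period more than twice". The count is of stops under the 13.1 criteria, so the rule takes effect at a third stop. The 13.1 criteria cover saturation, heart rate and metHb, and also "a change in the blood pressure systolic value" of 20 mmHg or more, and "a recorded inspired NO₂ > 5 ppm during any treatment".

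After an adverse-event withdrawal, 13.2 requires the event to be followed to resolution and adds that "the follow-up evaluations should be performed when the subject has stabilized". It does not define those evaluations. For any subject who does not complete, the reason is recorded.

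On cultures, section 12.4.1 states: "Sputum will be collected for culture at Screening, and Days 5, 12, and 19 (treatment dates), and Weeks 7, 11 and 15 (follow up"). Table 3-1 shows the same visits and has no early-termination column. Section 8 sets the endpoint: "The primary measure of efficacy will be sputum culture for mycobacteria converted to negative at completion of treatment". The last dosing day is C5, Day 19. Section 14.3.2 reports the proportion converted, and the synopsis adds exact binomial intervals. Neither says who is in the denominator or how a missing EOT culture is handled.

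**The concern.** Stopping a drug and leaving a study are different acts. A subject who cannot continue gNO can usually still give sputum at visits already in the calendar. The operative wording of 13.2 merges the two, and no other text keeps the subject on the culture schedule. A subject withdrawn before Day 19 may therefore have no primary outcome. One withdrawn before Day 5 may have no post-baseline culture at all.

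Two things are at stake. The first is the conversion rate in 6 to 10 subjects, where one lost culture is 10% of the primary data at n=10 and 17% (1/6) at n=6. The second is the Week 7, 11 and 15 cultures, the only post-treatment data on how long conversion lasts. Section 9.2 says the response rate and time to recurrence will inform the next trial. Because the trial is open-label and the investigator performs the analysis (section 14), an unstated denominator would be settled after the cultures are known.

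**Working it through.** **1. The plan's own figure.** Section 14.1 gives 0% to 31% for no responders among 10. The exact two-sided 95% upper limit for 0/n is 1 − 0.025^(1/n). For n = 10 this is 1 − 0.025^(0.1) = 30.8%, so the figure is reproduced.

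**2. Is the primary culture protected after a 13.2 withdrawal?** Each text that might protect it, in turn:

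- *Chapter 13 heading (withdrawal from treatment) and the 14.3.3.1 table of adverse events leading to treatment discontinuation.* Both recognise stopping treatment; neither says that cultures go on.
- *Follow-up evaluations in 13.2.* These plausibly mean the monthly visits of 9.1.3 (F1 to F3), which include cultures. They are not tied to Day 19, and they stand next to the text on adverse-event withdrawals.
- *Day 5 and Day 12 cultures.* These may exist, and 9.1 describes the short-term effect as conversion on treatment. No rule lets either stand for EOT.
- *Per-subject summaries (14.2).* These would show the gap but cannot fill it.

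The EOT culture is therefore unprotected. The follow-up cultures are uncertain.

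**3. Effect on precision if such subjects were dropped** (the plan does not say that they would be), with no responders:

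| n analysed | upper limit |
|---|---|
| 10 | 30.8% |
| 9 | 33.6% |
| 8 | 36.9% |

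**4. Effect on the rate.** Illustration: ten treated, two EOT cultures missing, six of the observed cultures negative.

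- Observed cases: 6/8 = 75% (exact 95% interval 34.9% to 96.8%).
- Missing counted as non-conversion: 6/10 = 60% (26.2% to 87.8%).
- Missing counted as conversion: 8/10 = 80% (44.4% to 97.5%).

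The all-treated rate is then known only to lie between 60% and 80%. Section 14.1 itself gives 6 of 8 as an example of a response high enough to limit the sample size, so the denominator affects how a result is read.

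**5. How often might the third-stop rule apply?** The documents give no stop rate, so this is a range under assumptions: the count runs over the whole course, and stops are independent with a constant chance p per inhalation. The course has 3 × 15 = 45 inhalations, and three stops are 3/45 = 6.7% of it. With X ~ Binomial(45, p), P = P(X ≥ 3), and the chance for at least one of 10 subjects is 1 − (1 − P)^10:

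| p (assumed) | P, one subject | at least one of 10 |
|---|---|---|
| 1% | 1.0% | 9.9% |
| 2% | 6.1% | 46.7% |
| 3% | 15.2% | 80.8% |

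The last column depends almost entirely on the assumed p. It shows sensitivity and is not a forecast.

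**6. What the documents suggest about p.** In the phase I summary (section 6), eight patients had metHb of at most 3.0% and saturation never below 95%. A peak of 3.0% cannot be a rise of more than 5%, and a fall from 100% to 95% is not more than 5 points, so neither criterion would have been met there. Those sessions lasted 30 minutes, against 50 here. The summary gives no blood pressure, heart rate or NO₂ stops.

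**The case against.** The strongest reply is that the wording is loose rather than harmful. The protocol has one block called follow-up, with monthly cultures, so the follow-up evaluations in 13.2 most naturally mean F1 to F3. Most 13.1 triggers are abnormal parameters that could be recorded as adverse events, and this would bring many third-stop subjects under the same sentence. This has force for Weeks 7 to 15. A reader might infer that those cultures are certainly lost, and the text does not support that. It does not reach Day 19.

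The second reply is that the triggers will rarely fire. Table 12.1 schedules blood pressure before an inhalation, at its end and 30 minutes later, but not during it, so a mid-inhalation blood pressure stop needs an unscheduled reading. Section 11.3 specifies a device that holds NO₂ at or below 3 ppm. Two compassionate-use patients received 72 and 90 inhalations, although their stop counts are not reported. A reader might infer that blood pressure or device events will remove many subjects; the documents give no basis for that. Nor does any single related adverse event cause withdrawal: it must be one of the listed events.

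Third, this is a small uncontrolled study without formal comparisons, and the precision loss in step 3 is modest. That is true, and it limits the seriousness. It does not excuse losing a primary outcome that could be collected at a scheduled visit.

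Fourth, the off-drug Day 19 culture may be the wrong primary measure. A subject stopped on Day 3 would be judged 16 days off drug, although the endpoint is set at completion of treatment. This stands: the choice between the stopping-time and the Day 19 culture is open, and the plan only needs to make it in advance.

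**Conclusion.** The point holds as a gap created by a stated rule. Following 13.2 as written can lose the EOT primary culture for subjects withdrawn before Day 19, and it leaves their Week 7, 11 and 15 cultures unsecured. The size per lost subject is 10% to 17% of the primary data. The frequency is unknown and may be low. The figures in steps 3 and 4 assume one or two lost cultures, and those in step 5 rest on assumed stop rates.

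A reader might infer that the conversion rate will be inflated. The documents do not support a direction: some triggers concern tolerance and others do not, and no completers-only analysis is stated. Safety reporting is not at issue, because adverse events, disposition and withdrawal reasons are still recorded. The change should be made because it is cheap and the primary outcome rests on so few subjects. Confidence is medium, mainly because the follow-up wording is ambiguous and the stop rate is not given.

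**What to change.** Keep all the stopping criteria, and make these changes:

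- **13.2:** state that a subject who meets a criterion permanently stops gNO but stays on the visit schedule unless consent is withdrawn.
- **Table 3-1 and 12.4.1:** add an early-stop column with a sputum culture at stopping when clinically safe, with no induction after significant hemoptysis. Continue the scheduled Day 19 and F1 to F3 cultures.
- **14.3.2:** take as denominator all subjects who received at least one inhalation. Count a missing EOT culture as non-conversion and show the observed-case rate beside it. State in advance which culture, stopping-time or Day 19, serves as EOT for early stoppers, and report the other as supportive.

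The cost is a few sentences, one table column, a few off-drug visits, one extra sputum culture per early stopper, and a reported rate that may be lower than the observed-case rate.
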